## 14.2 VISIT TIME WINDOWS

Tables 15.2–1 and 15.2–2 present visits assigned for efficacy and safety analyses and the corresponding range of treatment days (window) during which an actual visit may occur for the OLTP and DBTP respectively.

Derived Visit	Target Day	Analysis Visit Window			
Baseline		<= Day 0 ª			
Open-label Ti	Open-label Treatment Period (OLTP)				
Day 1	Day 1	Day 1			
D 7		Start: Day 2			
Day /	Day /	End: the Day 7 dosing (Visit 2) date or Day 10 (if no Day 7 dosing) b			
Weels 2	Day 14	Start: 1 day after the Day 7 window ends			
Week 2		End: the Week 2 (Visit 3) dosing date or Day 17 (if no Week 2 dosing) b			
Weels 2	Day 21	Start: 1 day after the Week 2 window ends			
WEEK 5	Day 21	End: the Week 3 (Visit 4) dosing date or Day 24 (if no Week 3 dosing) b			
Week 4	Day 28 Start: 1 day after the Week 3 window ends				
		End: the Week 4 (Visit 5) dosing date or Day 31 (if no Week 4 dosing) b			
Week 5	Day 35	Start: 1 day after the Week 4 window ends			
		End: the Week 5 (Visit 6) dosing date or Day 38 (if no Week 5 dosing) b			

Week 6	Day 42	Start: 1 day after the Week 5 window ends
		End: the Week 6 (Visit 7) dosing date or Day 45 (if no Week6 dosing) b
Week 7	Day 49	Start: 1 day after the Week 6 window ends
		End: the Week 7 (Visit 8) dosing date or Day 52 (if no Week 7 dosing) b
Week 8	Day 56	Start: 1 day after the Week 7 window ends
		End: the Week 8 (Visit 9) dosing date or Day 59 (if no Week 8 dosing) b
Week 9	Day 63	Start: 1 day after the Week 8 window ends
		End: the Week 9 (Visit 10) dosing date or Day 66 (if no Week 9 dosing) b
Week 10	Day 70	Start: 1 day after the Week 9 window ends
		End: the Week 10 (Visit 11) dosing date or Day 73 (if no Week 10 dosing) b
Week 11	Day 77	Start: 1 day after the Week 10 window ends
		End: the Week 11 (Visit 12) dosing date or Day 80 (if no Week 11 dosing) b
Week 12	Day 84	Start: 1 day after the Week 11 window ends
		End: the Week 12 (Visit 13) dosing date or Day 87 (if no Week 12 dosing) b
Week 13	Day 91	Start: 1 day after the Week 12 window ends
		End: the Week 13 (Visit 14) dosing date or Day 94 (if no Week 13 dosing) b
Week 14	Day 98	Start: 1 day after the Week 13 window ends
		End: the Week 14 (Visit 15) dosing date or Day 101 (if no Week 14 dosing) b
Week 15	Day 105	Start: 1 day after the Week 14 window ends
		End: the Week 15 (Visit 16) dosing date or Day 108 (if no Week 15 dosing) b
Week 16	Day 112	Start: 1 day after the Week 15 window ends
		End: End of OLTP (Randomization Date or Date of Early Termination Visit)

Derived Visit	Target Day	Analysis Visit Window			
Baseline		<= Day/Week 0 a			
Double Blind	Double Blind Treatment Period (DBTP)				
Day 1	Day 1	Date of first dosing of IP in DBTP (Visit 17)			
D 7	D 7	Start: Day 2			
Day /	Day /	End: the Day 7 dosing (Visit 18) date or Day 10 (if no Day 7 dosing) b			
W. 1- 2	5.44	Start: 1 day after the Day 7 window ends			
week 2	Day 14	End: the Week 2 (Visit 19) dosing date or Day 17 (if no Week 2 dosing) b			
W. 1-2	D	Start: 1 day after the Week 2 window ends			
week 5	Day 21	End: the Week 3 (Visit 20) dosing date or Day 24 (if no Week 3 dosing) b			
Week 4	Day 28	Start: 1 day after the Week 3 window ends			
		End: the Week 4 (Visit 21) dosing date or Day 31 (if no Week 4 dosing) b			
Week 5	Day 35	Start: 1 day after the Week 4 window ends			
		End: the Week 5 (Visit 22) dosing date or Day 38 (if no Week 5 dosing) b			
Week 6	Day 42	Start: 1 day after the Week 5 window ends			
		End: the Week 6 (Visit 23) dosing date or Day 45 (if no Week 6 dosing) b			
Week 7	Day 49	Start: 1 day after the Week 6 window ends			
		End: the Week 7 (Visit 24) dosing date or Day 52 (if no Week 7 dosing) b			
Week 8	Day 56	Start: 1 day after the Week 7 window ends			
		End: the Week 8 (Visit 25) dosing date or Day 59 (if no Week 8 dosing) b			
Week 9	Day 63	Start: 1 day after the Week 8 window ends			
		End: the Week 9 (Visit 26) dosing date or Day 66 (if no Week 9 dosing) b			
Week 10	Day 70	Start: 1 day after the Week 9 window ends			
		End: the Week 10 (Visit 27) dosing date or Day 73 (if no Week 10 dosing) b			
Week 11	Day 77	Start: 1 day after the Week 10window ends			
		End: the Week 11 (Visit 28) dosing date or Day 80 (if no Week 11 dosing) b			
Week 12	Day 84	Start: 1 day after the Week 11 window ends			
		End: the Week 12 (Visit 29) dosing date or Day 87 (if no Week 12 dosing) b			
Week 13	Day 91	Start: 1 day after the Week 12 window ends			
		End: the Week 13 (Visit 30) dosing date or Day 94 (if no Week 13 dosing) b			

Week 14	Dev 09	Start: 1 day after the Week 12 window and
WCCK 14	Day 98	Start. 1 day after the week 15 window ends
		End: the Week 14 (Visit 31) dosing date or Day 101 (if no Week 14 dosing) b
Week 15	Day 105	Start: 1 day after the Week 14 window ends
		End: the Week 15 (Visit 32) dosing date or Day 108 (if no Week 15 dosing) b
Week 16	Day 112	Start: 1 day after the Week 15 window ends
		End: the Week 16 (Visit 33) dosing date or Day 115 (if no Week 16 dosing) b
Week 17	Day 119	Start: 1 day after the Week 16 window ends
		End: the Week 17 (Visit 34) dosing date or Day 122 (if no Week 17 dosing) b
Week 18	Day 126	Start: 1 day after the Week 17 window ends
		End: the Week 18 (Visit 35) dosing date or Day 129 (if no Week 18 dosing) b
Week 19	Day 133	Start: 1 day after the Week 18 window ends
		End: the Week 19 (Visit 36) dosing date or Day 136 (if no Week 19 dosing) b
Week 20	Day 140	Start: 1 day after the Week 19 window ends
		End: the Week 20 (Visit 37) dosing date or Day 143 (if no Week 20 dosing) b
Week 21	Day 147	Start: 1 day after the Week 20 window ends
		End: the Week 21 (Visit 38) dosing date or Day 150 (if no Week 21 dosing) b
Week 22	Day 154	Start: 1 day after the Week 21 window ends
		End: the Week 22 (Visit 39) dosing date or Day 157 (if no Week 22 dosing) b
Week 23	Day 161	Start: 1 day after the Week 22 window ends
		End: the Week 23 (Visit 40) dosing date or Day 164 (if no Week 23 dosing) b
Week 24	Day 168	Start: 1 day after the Week 23 window ends
		End: the Week 24 (Visit 41) dosing date or Day 171 (if no Week 24 dosing) b
Week 25	Day 175	Start: 1 day after the Week 24 window ends
		End: the Week 25 (Visit 42) dosing date or Day 178 (if no Week 25 dosing) b
Week 26	Day 182	Start: 1 day after the Week 25 window ends
		End: the Week 26 (Visit 43) dosing date or Day 185 (if no Week 26 dosing) b
Week 27	Day 189	Start: 1 day after the Week 26 window ends

		End: the Week 27 (Visit 44) dosing date or Day 192 (if no Week 27 dosing) b
Week 28	Day 196	Start: 1 day after the Week 27 window ends
		End: the Week 28 (Visit 45) dosing date or Day 199 (if no Week 28 dosing) b
Week 29	Day 203	Start: 1 day after the Week 28 window ends
		End: the Week 29 (Visit 46) dosing date or Day 206 (if no Week 29 dosing) b
Week 30	Day 210	Start: 1 day after the Week 29 window ends
		End: the Week 30 (Visit 47) dosing date or Day 213 (if no Week 30 dosing) b
Week 31	Day 217	Start: 1 day after the Week 30 window ends
		End: the Week 31 (Visit 48) dosing date or Day 220 (if no Week 31 dosing) b
Week 32	Day 224	Start: 1 day after the Week 31 window ends
		End: the Week 32 (Visit 49) dosing date or Day 227 (if no Week 32 dosing) b
Week 33	Day 231	Start: 1 day after the Week 32 window ends
		End: the Week 33 (Visit 50) dosing date or Day 234 (if no Week 33 dosing) b
Week 34	Day 238	Start: 1 day after the Week 33 window ends
		End: the Week 34 (Visit 51) dosing date or Day 241 (if no Week 34 dosing) b
Week 35	Day 245	Start: 1 day after the Week 34 window ends
		End: the Week 35 (Visit 52) dosing date or Day 248 (if no Week 35 dosing) b
Week 36	Day 252	Start: 1 day after the Week 35 window ends
		End: the Week 36 (Visit 53) dosing date or Day 255 (if no Week 36 dosing) b
Week 37	Day 259	Start: 1 day after the Week 36 window ends
		End: the Week 37 (Visit 54) dosing date or Day 262 (if no Week 37 dosing) b
Week 38	Day 266	Start: 1 day after the Week 37 window ends
		End: the Week 38 (Visit 55) dosing date or Day 269 (if no Week 38 dosing) b
Week 39	Day 273	Start: 1 day after the Week 38 window ends
		End: the Week 39 (Visit 56) dosing date or Day 280 (if no Week 39 dosing) b
Week 40	Day 280	Start: 1 day after the Week 39 window ends
		End: the Week 40 (Visit 57) dosing date or Day 283 (if no Week 40

		dosing) b
Week 41	Day 287	Start: 1 day after the Week 40 window ends
		End: the Week 41 (Visit 58) dosing date or Day 290 (if no Week 41 dosing) b
Week 42	Day 294	Start: 1 day after the Week 41 window ends
		End: the Week 42 (Visit 59) dosing date or Day 297 (if no Week 42 dosing) b
Week 43	Day 301	Start: 1 day after the Week 42 window ends
		End: the Week 43 (Visit 60) dosing date or Day 304 (if no Week 43 dosing) b
Week 44	Day 308	Start: 1 day after the Week 43 window ends
		End: the Week 44 (Visit 61) dosing date or Day 311 (if no Week 44 dosing) b
Week 45	Day 315	Start: 1 day after the Week 44 window ends
		End: the Week 45 (Visit 62) dosing date or Day 318 (if no Week 45 dosing) b
Week 46	Day 322	Start: 1 day after the Week 45 window ends
		End: the Week 46 (Visit 63) dosing date or Day 235 (if no Week 46 dosing) b
Week 47	Day 329	Start: 1 day after the Week 46 window ends
		End: the Week 47 (Visit 64) dosing date or Day 332 (if no Week 47 dosing) b
Week 48	Day 336	Start: 1 day after the Week 47 window ends
		End: the Week 48 (Visit 65) dosing date or Day 339 (if no Week 48 dosing) b
Week 52	Day 364	Start: 1 day after the Week 48 window ends
		End: End of DBTP (Visit 69, the study exit date of DBTP)
Safety Follow-	up Period (SF	P)
Week 54	Day 378	Within the safety follow-up phase (Visit 70)
End of SFP:	Final or termination	ation visit during SFP

a Day 0 is the date of the first dose of study treatment; baseline is defined as the last non-missing observations prior to first dose of study treatment for the given treatment period.

b Dosing visit is the nominal visit reported in CRF. During the OLTP a patient is scheduled to receive the 1st dose on day 0 (Visit 1), the 2nd dose at week 1, and will be weekly administered until week 16. If a patient skipped a scheduled re-treatment dosing at a week, the dosing date will be treated as missing for that week. During the DBTP a patient is schedule to receive the 1st dose on day 0 (Visit 17), the 2nd dose at week 1, and will be weekly administered until relapse criteria are met or for up to 52 weeks (Visit 69) or study termination.

If a patient has 2 or more values for a given endpoint within the same window, the value with collection date closest to the scheduled day will be used for analysis; if there are 2 values whose collection dates are equidistant from the scheduled day, the value corresponding to the later date will be used for analysis.

With the exception of endpoints recorded pre or post IP dose and Visit 69/ET MADRS assessments, in the event there are multiple values of the same endpoint on the same date, the last value will be taken as the value for that date. For endpoints reported pre IP dose, in the event there are multiple values of the same endpoint prior to IP dose, the last value prior to the IP dose is taken as the pre-dose value for that date. Similarly, for endpoints reported post IP dose, in the event there are multiple values of the same endpoint after IP dose, the last value will be taken as the post-dose value for that date. For multiple MADRS assessments on the same date for Visit 69/ET, the last MADRS assessment prior to Visit 69/ET on that date will be taken as the value for that date.

The first relapse date for a patient is defined as the earliest assessment date in which any of the relapse criteria mentioned above were met, obtained either from the date recorded on the Relapse CRF (for the primary reasons of "Risk of Suicide", "Need for hospitalization due to worsening of depression" or "Need for alternative treatment for depressive symptoms") or the dates of the corresponding MADRS or CGI-S assessments. For the relapses based on MADRS total score  $\geq 18$  at 2 consecutive visits, the relapse date is defined as the assessment date of the first visit of the 2 consecutive assessments.

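### The double-blind visit-window table has no rows for Weeks 49 to 51 and misprints two skipped-dose end days, so by-visit summaries built on it would misfile some values

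*SAP*

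**What the plan says.** SAP Section 14.2 sets the analysis visit windows for both efficacy and safety. In the double-blind table each weekly window closes on that week's dosing date or, if the dose was not given, on a printed fallback day. The next window opens the day after. Footnote b says how a missed dose is handled: "If a patient skipped a scheduled re-treatment dosing at a week, the dosing date will be treated as missing for that week".

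- **Last row.** Weekly rows run to Week 48 (Visit 65). The next row is Week 52, target Day 364: "Start: 1 day after the Week 48 window ends". It closes at "End of DBTP (Visit 69, the study exit date of DBTP".
- **Dosing schedule.** Footnote b says double-blind treatment "will be weekly administered until relapse criteria are met or for up to 52 weeks (Visit 69) or study termination". Protocol Section 9.1.2 requires a clinical assessment using MADRS and CGI-S at every double-blind visit.
- **Week 39** (target Day 273) closes at "the Week 39 (Visit 56) dosing date or Day 280 (if no Week 39 dosing").
- **Week 46** (target Day 322) closes at "the Week 46 (Visit 63) dosing date or Day 235 (if no Week 46 dosing").
- **Several values in one window:** "the value with collection date closest to the scheduled day will be used for analysis".
- **Day numbering.** The table's Day 1 row is the date of first double-blind dosing (Visit 17). Footnote a says "Day 0 is the date of the first dose of study treatment", and footnote b also puts Visit 17 on Day 0.

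**The concern.** Visit 65 is Week 48 and Visit 69 is Week 52, so Visits 66, 67 and 68 are Weeks 49, 50 and 51. They produce data but have no derived visit, and everything after Week 48 falls into a window labelled Week 52.

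The two odd fallback days break a pattern that every other weekly row follows. One of them closes a window before it opens. The Day 0/Day 1 conflict matters because it decides whether the Week 39 misprint does any damage.

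At stake is the accuracy of any by-visit table. Some values would be dropped and some would appear under the wrong week.

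**Working it through.** **1. Fallback end days.** Target day = 7 × week. The printed fallback end is target + 3 in 46 of the 48 weekly rows (Day 7, which is Week 1, to Week 48). For example, Week 38 is 266 + 3 = 269, as printed. The exceptions are:

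| Week | Target | Target + 3 | Printed |
|---|---|---|---|
| 39 | 273 | 276 | 280 |
| 46 | 322 | 325 | 235 |

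**2. Windows from the printed rules, other doses on schedule.** The dose day in week w is 7w if the first dose is Day 0, and 7w + 1 if it is Day 1.

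| Case | First dose = Day 0 | First dose = Day 1 |
|---|---|---|
| No dose skipped: Week 52 | Days 337–364 | Days 338–365 |
| Week 39 skipped: Week 39 | Days 267–280 | Days 268–280 |
| Week 39 skipped: Week 40 | 281 to 280 (empty) | Day 281 |
| Week 46 skipped: Week 46 | 316 to 235 (empty) | 317 to 235 (empty) |

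- *Week 52.* The window has 364 − 337 + 1 = 28 days under Day 0, and also 28 under Day 1. A completer's values on Days 343, 350 and 357 (or 344, 351 and 358) compete with the Visit 69 value under the closest-value rule and lose. The completer's own Week 52 value is correct.
- *Week 39 dose skipped.* Under Day 0 numbering, an on-time Week 40 value on Day 280 is filed as Week 39. Under Day 1 numbering, both on-time values file correctly.
- *Week 46 dose skipped.* Week 47 then opens on Day 236 and absorbs the Week 46 value. Distances from target Day 329 are |322 − 329| = 7 against 0 for an on-time Week 47 value (Day 0 numbering), or |323 − 329| = 6 against |330 − 329| = 1 (Day 1 numbering). Either way the Week 46 value is dropped if the on-time Week 47 value exists. Week 47 also overlaps Weeks 34 to 45, but those weeks keep their on-target values. If the Week 46 assessment was missed along with the dose, nothing is lost.

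**3. How many patients the Week 52 window touches.** Inputs from SAP Section 12.0: 19% placebo relapse and 20% dropout per 26 weeks, hazard ratio 0.475, 200 per arm. Assumptions: constant hazards, and 0.475 in both rapastinel arms.

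- Placebo relapse hazard: −ln(0.81)/26 = 0.00810 per week
- Rapastinel relapse hazard: 0.475 × 0.00810 = 0.00385 per week
- Dropout hazard: −ln(0.80)/26 = 0.00858 per week
- On study at week t: 200·exp(−0.01669t) + 400·exp(−0.01243t)

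| Time | On study |
|---|---|
| Week 48 | 310.0 |
| Week 51 | 297.6 |
| Week 52 | 293.5 |

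Exits between Weeks 48 and 51: 310.0 − 297.6 = 12.4 (4.6 relapses, 7.8 dropouts). Exits between Weeks 48 and 52: 310.0 − 293.5 = 16.5 (6.1 relapses, 10.4 dropouts). If only 300 were randomized, these halve to about 155 on study at Week 48, with 6.2 and 8.2 exits. All exit counts are upper bounds, because a dropout with no assessment after Week 48 has no value to mislabel.

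**4. Check of the correction.** With rows for Weeks 49 to 51 and end days 276 and 325, every on-time weekly value files in its own week under both conventions. Under Day 0 with no dose skipped, the windows are Week 49 = Days 337–343, Week 50 = 344–350, Week 51 = 351–357 and Week 52 = 358–364.

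**The case against.** The strongest reply is that Week 52 is partly the name of the exit visit. Protocol Section 9.1.1 and SAP Section 2.0 use Visit 69/Week 52 for end-of-treatment or early-termination assessments whatever the calendar week, and the final window closes at study exit. On that reading, an exit assessment in Weeks 49 to 51 belongs in the last row, and pooling may be intended. This does not clear the table. Its windows are set by calendar day, so a patient who exits at Week 30 is filed under Week 30, and only exits in Weeks 49 to 51 are relabelled Week 52. No pooling is stated, and pooling would explain neither misprint nor the day-numbering conflict.

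The second reply is that nothing visible is harmed, and most of this stands. SAP Section 14 dates relapse from actual assessments or the relapse form, so the Kaplan-Meier analysis does not depend on the windows. Section 14.4 uses all postbaseline values for potentially clinically significant findings and lists every assessment. Section 15.0 cuts output to what an abbreviated report needs, and no by-visit efficacy table can be seen.

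Third, the misprints act only when the Week 39 or Week 46 dose is skipped, which may often mean a missed visit with no value to misfile. A programmer would probably notice that a window ending on Day 235 cannot be right. That is fair, and the documents give no skipped-dose rate. Digits can also be corrupted when a PDF is read as text, and the Week 14 row shows signs of this. The Week 39 and Week 46 rows are otherwise intact, but both end days should be checked against the source.

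**Conclusion.** The concern holds and is minor. Followed as written, the table gives Weeks 49 to 51 no derived visit, makes the Week 52 window 28 days long, and contains one impossible end day and one that falls on the following week's target. Every completer would lose three weekly values from a by-visit summary. At most about 12 to 16 patients could have an earlier last value shown as Week 52, given 600 randomized and the plan's own rates. The Week 46 misprint misfiles a value under either day convention, but only if that dose is skipped and the assessment is still done. The Week 39 misprint misfiles an on-time Week 40 value only if the first dose is Day 0, and the table and its footnotes do not agree on that.

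**What to change.** - Add rows for Week 49 (Visit 66, target Day 343, skipped-dose end Day 346), Week 50 (Visit 67, 350, 353) and Week 51 (Visit 68, 357, 360). Start Week 52 the day after the Week 51 window closes.
- If one pooled final window is intended, say so and label it end of treatment instead of Week 52.
- After checking the source document, change the Week 39 and Week 46 skipped-dose end days to 276 and 325.
- State one day-numbering convention and use it in the table and both footnotes.

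The cost is an edit to one SAP table and a rerun of the windowing code. Data collection does not change.

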- Need for alternative treatment of depressive symptoms as determined by the investigator

Upon meeting any of the relapse criteria at any visit in the DBTP, the patient will be considered a completer and the Visit 69/ET Visit procedures should be conducted.

Each randomized patient will be treated until relapse criteria are met, or until he/she has completed 52 weeks of double-blind treatment or discontinued for other reasons. The study will be terminated when all randomized patients have either met relapse criteria, early terminated for other reasons, or completed 52 weeks of the DBTP and completed the safety-follow up period where appropriate.

Upon completion of the DBTP, patients will enter a 2-week safety follow-up period.

[figure not shown]

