#### 8.0 EFFICACY ANALYSES

#### 8.1 PRIMARY EFFICACY PARAMETERS

The analysis of the primary efficacy parameter will be performed using the Double-blind mITT Population.

The primary efficacy parameter is the time to first relapse during the 52 weeks of the DBTP, defined as the number of days from the randomization date of DBTP to the relapse date (ie., relapse date – randomization date + 1). Relapse during the DBTP is defined as meeting any of the following criteria:

- Rater-administered MADRS total score  $\geq 18$  at 2 consecutive visits
- $\geq 2$  increase in CGI-S score compared with that obtained at randomization
- Risk of suicide as determined by the investigator
- Need for hospitalization due to worsening of depression as determined by the investigator
- Need for alternative treatment of depressive symptoms as determined by the investigator

Patients who did not meet the above relapse criteria during the 52 weeks of the DBTP, the time to relapse will be censored at the time of completion or discontinuation from the study, or 52 weeks, whichever is earlier.

The primary efficacy analysis will be presented by the cumulative distribution function of time to relapse characterized by the Kaplan-Meier curve for each treatment group.

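### The SAP's same-date rule protects the exit-day MADRS but not the CGI-S, so if CGI-S is rated again at ET, a lower repeat could remove a CGI-S-only relapse from the primary endpoint.

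*SAP*

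**What the plan says.** SAP section 14.2 sets a rule for repeated ratings on one date: "multiple values of the same endpoint on the same date, the last value will be taken as the value for that date". The rule opens with its exceptions: "With the exception of endpoints recorded pre or post IP dose and Visit 69/ET MADRS assessments". For pre-dose endpoints, "the last value prior to the IP dose is taken as the pre-dose value for that date". For MADRS on the exit date, "the last MADRS assessment prior to Visit 69/ET on that date will be taken as the value for that date". CGI-S is not named.

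The same part of the SAP dates the relapse: "The first relapse date for a patient is defined as the earliest assessment date in which any of the relapse criteria mentioned above were met". The date on the Relapse CRF serves only the three investigator-judged reasons (suicide risk, hospitalization, alternative treatment). Relapses on the rating scales are dated from the ratings themselves: "or the dates of the corresponding MADRS or CGI-S assessments".

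Under SAP section 8.1, MADRS relapse needs 2 consecutive visits. CGI-S relapse needs one score, a 2-point or larger "increase in CGI-S score compared with that obtained at randomization". A patient with no derived relapse is censored at completion, discontinuation or 52 weeks, whichever comes first.

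Protocol section 9.1.2 says that a patient who meets a relapse criterion at any visit is "considered a completer and the Visit 69/ET Visit procedures should be conducted".

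**The concern.** Two scales define relapse, and on the exit date the SAP treats them differently. For MADRS it keeps the rating made before Visit 69/ET. For CGI-S the general rule keeps the last rating of the day, which would be the ET rating if there is one. CGI-S is the scale on which a single replaced value can decide the event, because no confirming visit is required.

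At stake is the classification of a primary event. A patient whose treatment ended because of a CGI-S rise could appear in the data as an early completer with no relapse, censored on the day the relapse was declared. Censoring of that kind is informative, because it happens precisely to patients who met the criterion.

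**Working it through.** **Step 1. What must happen for an event to be lost.** All four conditions are needed.

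1. *A second CGI-S is recorded on the relapse date.* Protocol 9.1.2 uses the change in CGI-S at every double-blind visit to judge stability, so a CGI-S exists at the visit. It then calls for the Visit 69/ET procedures. Protocol 9.3.3 defines the final assessment as all evaluations scheduled for Visit 69. A repeat is therefore implied, but the Schedule of Evaluations is not shown and this cannot be confirmed.
2. *The repeat is less than 2 points above the randomization score.* The documents give no rate for this.
3. *The relapse derivation uses the one retained value per date.* The SAP neither states nor excludes this.
4. *No other relapse criterion is met.* The Relapse CRF date cannot help, because it is not a source for CGI-S relapses.

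The pre-dose exception helps only if a dose falls between the two ratings. Protocol 9.4.1 puts efficacy ratings before the dose, and a footnote in SAP 14.2 describes weekly dosing as continuing until relapse criteria are met. With no dose in between, that exception does not protect the earlier score.

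**Step 2. Reproduce the plan's power.** Inputs from SAP section 12.0: 200 per group, 19% placebo relapse and 20% dropout per 26 weeks, hazard ratio 0.475, alpha 0.05 (two-sided per Protocol 9.7.5), 52 weeks. I assume constant hazards per 26-week unit:

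- Placebo relapse hazard: −ln(0.81) = 0.2107. Rapastinel: 0.475 × 0.2107 = 0.1001. Dropout: −ln(0.80) = 0.2231.
- Expected events per arm = 200 × λ/(λ+δ) × [1 − exp(−2(λ+δ))], where λ is the relapse hazard and δ the dropout hazard.
- Placebo: 200 × 0.2817 = 56.3. Rapastinel: 200 × 0.1474 = 29.5. Total: 85.8.
- Freedman power = Φ(√D × (1 − HR)/(1 + HR) − 1.96), where D is the total number of events. This gives Φ(9.265 × 0.3559 − 1.96) = Φ(1.338) = 0.910.

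The stated 90% is reproduced. Schoenfeld's formula gives 0.932, and a simulated log-rank test (6,000 runs) gives 0.925.

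**Step 3. Effect of losing a share f of events.** Here f is an assumption, taken as equal in all arms. It is the product of three unknowns: the share of relapses resting on CGI-S alone, the share of those with a same-day repeat, and the share of repeats that fall below the threshold. For illustration, if every such relapse had a repeat, 25% × 5% = 1.25% and 50% × 10% = 5%. Placebo relapse at 52 weeks is 1 − 0.81^(2(1−f)).

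| f | Events lost | Events left | Freedman power | Placebo 52-week relapse |
|---|---|---|---|---|
| 0 | 0 | 85.8 | 0.910 | 34.4% |
| 1% | 0.9 | 85.0 | 0.907 | 34.1% |
| 5% | 4.3 | 81.5 | 0.895 | 33.0% |
| 10% | 8.6 | 77.3 | 0.879 | 31.6% |

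With equal f, about two thirds of the lost events (56.3/85.8 = 66%) are on placebo, and the expected hazard ratio does not change. Power here refers to the log-rank test in Protocol 9.7.5.1. Under SAP sections 8.1 and 15.0 the primary analysis is the Kaplan-Meier curve alone, so the effect there is a slightly lower curve.

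**The case against.** The strongest reply is that nothing is erased. The relapse date is the earliest assessment date on which any criterion was met. That wording tests ratings against criteria and does not mention a retained daily value. The same-date rule sits among the visit-window conventions and may serve only the by-visit summaries. This reading is tenable. It is not the only one: where the SAP wants all ratings used despite repeats it can say so, as section 14.4 does for potentially clinically significant safety values, and it does not say so here. Two programmers could build different primary endpoints from this text.

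A second reply is that the MADRS exception may be deliberate. A same-day ET repeat might be miscounted as the second of two consecutive MADRS scores, a problem that CGI-S does not have. CGI-S may also be rated only once that day. Both are possible, and nothing visible settles them.

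A reader might infer from the text that the SAP expects same-day CGI-S duplicates and therefore does discard CGI-S relapses. The documents show an expectation of duplicates for MADRS only. A reader might also see an error in the opposite case, where a patient leaving for another reason becomes a relapse on the ET rating alone. That patient has a score meeting the stated criterion, so counting the event agrees with SAP 8.1.

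**Conclusion.** The gap is real but conditional. On a plain reading, the general same-date rule covers CGI-S on the exit date, and the text does not exclude its use in deriving relapse. If CGI-S is repeated at ET and the rule is used that way, a lower repeat turns a CGI-S-only relapse into a censored time. The documents do not support the stronger statement that events will be lost.

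The size is unknown and probably small. Losing 1% to 5% of about 86 events means about 1 to 4 events per comparison and Freedman power of 0.907 to 0.895 against 0.910. That range rests on an assumed loss rate, equal across arms, and on constant hazards. It is a cheap improvement to a primary-endpoint rule, and it changes no figure stated in the documents.

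**What to change.** Add to SAP section 14.2, beside the relapse-date definition, a sentence to this effect: the same-date selection rule does not apply to the CGI-S relapse criterion; any CGI-S rating in the double-blind period, at a scheduled visit or at Visit 69/ET, that is at least 2 above the randomization score counts as a relapse on that assessment date.

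This is better than simply adding CGI-S to the MADRS exception. That wording would discard an ET rating that meets the criterion whenever an earlier rating the same day did not, and so could remove a qualifying relapse.

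The cost is one sentence and a small programming change. The downside is that a same-day ET rating alone can count as a relapse, which agrees with the criterion as stated. If CGI-S turns out to be rated only once on the exit date, the sentence does no harm.
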